## 2 Objectives and endpoints

**Table 2-1 Objectives and related endpoints**

Primary Objective	Endpoints
To determine the safety and tolerability of single or combination therapy during 12 weeks of treatment	Safety endpoints (including vital signs, physical examination, laboratory measurements, ECG); Adverse events
Secondary Objectives	Endpoints
To determine the effect of single or combination therapy on circulating markers of ongoing liver fibrosis	Enhanced Liver Fibrosis (ELF) Test
To determine the effect of single or combination therapy on intrahepatic lipid content	Percent (%) liver fat as measured by Magnetic Resonance Imaging-Proton Density Fat Fraction (MRI-PDFF)
To determine the effect of single or combination therapy on cardiometabolic risk parameters	Body weight, waist and hip circumference, waist-to-hip ratio, Homeostasis Model Assessment of Insulin Resistance (HOMA-IR), hemoglobin A1c (HbA1c), fasting glucose, fasting insulin, fasting lipid profile
To determine the effect of single or combination therapy on circulating markers of liver and/or systemic inflammation	Liver function test (ALT), high-sensitivity C-reactive Protein (hsCRP)
To evaluate the pharmacokinetics (PK) of each individual agent when administered as a single or combination therapy	Plasma concentrations
Exploratory Objectives	Endpoints
Commercially Confidential Information	

### 3 Study design

This is a non-confirmatory, multicenter, open label, platform study in NAFLD patients with a NASH-like biomarker phenotype.

Commercially Confidential Information

There is a maximum of five cohorts planned. Each cohort will consist of a 33-day screening period (Day -60 to Day -28), a baseline period of 27 days (Day -27 to Day -1), a treatment period of 12 weeks (Day 1 to Day 85), and a study completion evaluation (End of Study [EOS] 1) approximately 28 days after the last drug administration (Day 113).

Commercially Confidential Information

Participants will be advised to maintain their recommended diet for NAFLD during the study. The study design scheme is shown below in [Figure 3-1](#):

**Figure 3-1** Study design

EOS = End of Study

ARandomization for any patient can occur after informed consent is obtained and eligibility is confirmed, ideally as close to Day 1 as possible. Patients will be randomized into any of the treatment arms open to enrolment for which the patient meets the eligibility criteria.

BTreatment arm(s) will be defined for each cohort.

CEOS2 visit only required for treatments with an extended half-life. For all other treatments, EOS1 will serve as the EOS visit.

Participants who meet the eligibility criteria at screening will have baseline assessments performed, including determination of the percent liver fat content by MRI.

Once eligibility has been confirmed from screening and baseline assessments, participants will be randomized into any of the treatment arms open to enrollment for which the participant meets the eligibility criteria using an Interactive Response Technology (IRT) system. If a participant does not meet the specific eligibility criteria of a particular treatment arm, the participant will be randomized to any open and actively enrolling arms for which the participant is eligible. Randomization will be stratified by race and BMI (refer to [Section 6.3.2](#)). In the event that there

is only one open treatment arm in a cohort or if participants are only deemed eligible for one treatment arm, participants will be enrolled using the same IRT system, but without randomization.

The first dose of study medications will be administered to participants during the visit on Day 1, and scheduled assessments will be performed as defined in the [Assessment schedule](#).

For orally-administered study medications, the first dose will be administered under fasted conditions at the visit on Day 1. Also, participants will be provided with a supply for -self administration during the treatment period on non-visit days. On visit days, study medication will be administered by study staff. In the event that multiple doses are needed per day, the participant can also self-administer subsequent doses after the initial dose is administered by study staff. For other types of study medications, such as injectable monoclonal antibodies, dose administration will be managed by study staff on designated visit days. Detailed instructions for taking/administering study treatment will be provided in the cohort-specific sections and/or the SOM.

If adverse events or significant laboratory abnormalities are noted, in addition to dose reduction or interruption of the investigational drug(s), the investigator may choose to place the participant under a period of close observation until the participant is deemed to have returned to a satisfactory state of health in the opinion of the investigator. In the case of liver or renal laboratory abnormalities, please see [Section 16.1](#) and [Section 16.2](#), respectively, for additional information.

Safety assessments will include physical examinations, ECGs, vital signs, standard clinical laboratory evaluations (hematology, blood chemistry, urinalysis), adverse event and serious adverse event monitoring.

Refer to the [Assessment schedule](#) for details of safety, PK, biomarker and PD assessments.

Please refer to [Section 9.3](#) for details regarding the end of the study.

## **Remote procedures**

At the investigator's discretion, and based on benefit-risk considerations of the participant's clinical condition, qualifying participants may be offered the option to have certain clinical trial procedures according to [Table 8-1](#) performed at a remote location. Procedures may be performed remotely under the oversight of the Investigator, who retains accountability for oversight and all efficacy and safety decisions with delegation of tasks to an off-site healthcare professional (OHP). In addition to procedures performed by the OHP, the on-site staff may support certain assessments using tele-visits.

The remote procedures will only be offered in certain countries and sites as determined by Novartis based on national and local regulations. The OHPs will be provided by a third-party vendor sourced by Novartis. Where a site wishes to use OHPs that are not provided by Novartis, this must be agreed upon with Novartis prior to use.

## 4 Rationale

### 4.1 Rationale for study design

The NEXSCOT study is designed to safely allow rapid and efficient determination of potential high efficacy drugs and drug combinations in participants with NAFLD and a NASH-like (biomarker) phenotype. Rationale for key aspects of this design are provided below.

#### 4.1.1 Platform study

Commercially Confidential Information

The cohort-specific modules ([Section 17](#)) will contain the mechanism of action, non-clinical information, proposed dose and dosing regimen, and rationale for each treatment arm including anticipated safety, potential drug-drug interactions, unique inclusion or exclusion criteria, unique stopping rules or dose reduction criteria and other treatment specific information.

#### 4.1.2 Study population

The study enrolls NAFLD patients with characteristics consistent with NASH:

- Two risk factors for NASH: elevated BMI and history of Type II diabetes mellitus, and
- Three phenotypic biomarkers for NASH as shown in [Table 4-1](#): elevated liver fat content diagnostic of NAFLD as measured by MRI-PDFF, liver inflammation as measured by ALT, and liver fibrosis as measured by ELF Test. These phenotypic biomarkers are consistent with the pathobiology of NASH and recent studies have supported these biomarkers as being highly predictive of NASH ([Harrison et al 2018a](#); [Sanyal et al 2017](#)).

**Table 4-1 Biomarker inclusion criteria compared to normal range**

[figure not shown]
	ALT	Liver fat content (MRI-PDFF)	ELF Test
Normal value	29-33 IU/L (males) 19-25 IU/L (females)	< 5%	< 7.7
NEXSCOT inclusion criteria	≥ 43 IU/L and ≤ 5x ULN (males) ≥ 28 IU/L and ≤ 5x ULN (females)	≥ 8%	8.5-10.5
Reference	Kwo et al 2017	Petäjä and Yki-Järvinen 2016	Lichtinghagen et al 2013 , Vilar-Gomez and Chalasani 2018

In this study, ELF Test measurement will be conducted at screening (see [Section 5.1](#) Inclusion criteria), and participants with an ELF Test result within the range of 8.5-10.5 will be

eligible for participation in the study. The goal of using these ELF Test inclusion criteria is to enrich the study population for those subjects with a high likelihood of an ongoing fibrotic process in the liver (disease stage F1-F3) but do not yet have severe fibrosis or cirrhosis (stage F4). This ELF Test inclusion range is based on a weight-of-evidence analysis of the following reports:

- In their review of the current state-of-the-art of soluble liver fibrosis biomarkers, ([Vilar-Gomez and Chalasani 2018](#)) noted that the area under the receiver operating characteristic curve (AUROC) for ELF Test using 8.5-10.18 cut-off values to detect liver fibrosis ( $F \geq 2$ ) was 0.82 in a meta-analysis of adult and pediatric patients (n=1329) with chronic liver disease, including NAFLD.
- ([Lichtinghagen et al 2013](#)) proposed the following ELF Test cut-off values based on the results of this test in healthy volunteers (n=400) and the relationship of this test with liver biopsy staged fibrosis in patients with hepatitis C (n=39):
  - $\leq 7.7$  excluded fibrosis with high sensitivity
  - $\geq 9.8$  had high specificity for identification of fibrosis
  - $\geq 11.3$  discriminated cirrhosis
- ([The National Institute for Health and Care Excellence 2016](#)) proposed that NAFLD patients should have ELF Test as a measure of advanced liver fibrosis and proposed that a value of  $\geq 10.51$  was consistent with advanced liver fibrosis.
- ([Gungoren et al 2018](#)) showed that using an ELF Test cut-off of  $\geq 8.84$  was associated with a liver fibrosis score of  $F \geq 2$  at an AUROC of 0.89 in 46 patients with auto-immune hepatitis who have liver biopsy.
- As shown in [Figure 4-1](#), ([Nobili et al 2009](#)) reported a step-wise relationship of liver biopsy measured fibrosis stage to ELF Test result in 121 patients with NAFLD.

**Figure 4-1 Relationship of fibrosis state and ELF Test result**

Source: ([Nobili et al 2009](#)).

This study does not require the invasive procedure of liver biopsy in order to confirm NASH. However, based on the biomarkers evaluated at screening and respective inclusion criteria, in particular ELF Test scores, it can be reasonably assumed that a large proportion of participants enrolled in this study will indeed have NASH ([Lopez et al 2017](#)). Patients with ELF Test > 10.5 and ALT > 5x ULN will not be enrolled given that these highly elevated values are consistent with severe and potentially intractable liver fibrosis / cirrhosis and/or inflammation.

#### **4.1.3 Objectives (Endpoints)**

Given that NEXSCOT will be studying investigational drugs used in combination for the first time, safety and tolerability will be the paramount and primary objective, assessed by safety endpoints (including vital signs, physical examination, laboratory measurements, ECG) and adverse events (see [Section 12.4](#)).

Secondary objectives are included in [Table 2-1](#). The secondary endpoints are (see [Section 12.5](#)):

- ALT, % liver fat (MRI-PDFF), and ELF Test: These biomarkers will provide evidence of efficacy and are further described below.
- Cardiometabolic risk factors: NAFLD and NASH patients are at high risk for cardiovascular morbidity and mortality. Therefore, it is important to characterize any negative or positive effects of single drugs or drug combinations on cardiometabolic risk factors including body weight, waist and hip circumference, waist-to-hip ratio, Homeostasis Model Assessment of Insulin Resistance (HOMA-IR), hemoglobin A1C (HbA1c), fasting glucose, fasting insulin, and fasting lipid profile.
- Pharmacokinetics: The potential pharmacokinetic interactions of drugs used in combination will be measured.

Commercially Confidential Information

Currently, there are no approved treatments for NASH. However, over the last five years, the results of a number of studies in this indication have been reported in the medical literature ([Sanyal et al 2017](#); [Harrison et al 2018a](#); [Harrison et al 2018b](#)). Based on these results, considerable knowledge of the magnitude of both placebo and active treatment effects in NASH studies now exists.

The placebo effects reported in four relatively short-term ( $\leq 16$  week) NASH studies for three main efficacy endpoints, ALT, % liver fat (MRI-PDFF), and ELF Test, are summarized in [Table 4-2](#).

**Table 4-2 Examples of placebo effect in published studies in NASH and NASH-like patient populations**

Investigational drug	Obeticholic acid (n=23)	Obeticholic acid (n=142)	NGM282 (n=27)	MGL3196 (n=42)	BMS986036 (n=26)
Duration (weeks)	6	12	12	12	16
%Δ ALT from baseline	35.5	-13.4	-2.2	-	-4.5
Relative %Δ liver fat from baseline	-	-	-3.0	-9.6	-
Δ ELF Test from baseline	0.3	-	0	0.1	-
Reference	Mudaliar et al 2013	Neuschwander-Tetri et al 2015	Harrison et al 2018a	Harrison et al 2018b, Abstract GS-009	Sanyal et al 2017

Commercially Confidential Information

Conversely, a review of multiple, recent studies in patients with NASH or a NASH-like (biomarker) phenotype shows that high efficacy, active treatment is associated with relative percent decreases in % liver fat (MRI-PDFF) and ALT of  $\geq 30\%$  ([Sanyal et al 2017](#); [Harrison et al 2018a](#); [Harrison et al 2018b](#)). Similarly, a decrease in ELF Test by  $\geq 0.3$  units or 3% can be considered evidence of a substantive, beneficial reversal in the ongoing liver fibrotic process ([Harrison et al 2018a](#)).

Commercially Confidential Information

Commercially Confidential Information

#### **4.1.5 Follow-up period**

All participants receiving treatment in the NEXSCOT study should have safety evaluations and collection of concomitant treatments and/or adverse event data until at least approximately 28 days (Day 113) or, if applicable, until at least approximately 56 days (Day 141) after the last dose of study treatment. Please refer to [Section 9.1.1](#) for details pertaining to early study discontinuation and associated safety follow-up.

Commercially Confidential Information

---

Commercially Confidential Information

## **4.2 Rationale for dose/regimen and duration of treatment**

Please refer to [Section 17](#) (cohort-specific information) for a detailed rationale of each drug or drug combination treatment.

In general, the dose(s) of the drug(s) to be studied will be chosen based on an evaluation of all available preclinical and/or clinical data to ensure 1) a high likelihood of target or pathway modulation and 2) reasonable safety and tolerability.

Over the last five years, many exploratory studies in NASH have used a twelve-week duration of treatment, for example, ([Mudaliar et al 2013](#)) and ([Neuschwander-Tetri et al 2015](#)). Twelve weeks is considered the shortest treatment period that will allow measurable changes in improvement of endpoints such as liver inflammation, liver fat content and liver fibrosis.

## **4.3 Rationale for choice of control drugs (comparator/placebo) or combination drugs**

There is currently no appropriate comparator for use in the NASH/NAFLD patients.

Commercially Confidential Information

---

Commercially Confidential Information

While the primary purpose of NEXSCOT is to detect high efficacy drug combinations, single drug treatment arms may also be studied in those situations where the efficacy of the particular drug on the relevant endpoint biomarkers in the relevant patient population has not been previously measured. In this case, the treatment effects of the single drug treatment arm would be compared to both the combination drug effects and the historical placebo effects.

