------------------------	---

Study treatment	
Cohort 1 consists of two treatment arms:
 
 
• Arm 1: LYS006 CCI
 
• Arm 2: Tropifexor (LJN452) CCI + LYS006 CCI
 
 
Participants will be randomized into any of the treatment arms open to enrollment for which the participant meets the eligibility criteria. Randomization will be stratified by race and body mass index (BMI).
 
Multiple arms/cohorts are planned and future therapies will be introduced in subsequent protocol amendments.

Efficacy/ Pharmacodynamic (PD) assessments	
 
• Liver function tests and liver and/or systemic inflammation markers
 
• Markers of liver fibrosis (including ELF Test)
 
• Magnetic Resonance Imaging (MRI)
 
• Cardiometabolic risk parameters
 

Pharmacokinetic assessments	
 
• Plasma concentrations for tropifexor and LYS006 (Cohort 1)
 

Key safety assessments	
 
• Vital signs
 
• Physical examination
 
• Laboratory measurements
 
• ECG
 

Other assessments	Commercially Confidential Information
Data analysis	
Safety data will be summarized using descriptive statistics.
 
A mixed-effect model for repeated measures (MMRM) analysis will be conducted for log-transformed ratio to baseline ELF Test and ALT. The model will include effects for treatment, visit, treatment by visit interaction, stratification factor (race and BMI group), log-transformed baseline, and log-transformed baseline by visit interaction. An unstructured variance-covariance matrix will be used to account for correlation among multiple measurements from the same participant and variance heterogeneity. If the unstructured covariance causes model convergence issues then other simpler covariance structures will be considered. Least squares mean, the associated 2-sided 80% confidence interval and the p-value will be obtained for each treatment at each visit and back transformed to the original scale. Contrasts assessing trend over time will be constructed for each treatment using various functional forms as needed. Both cohort-wise and combined cohort analysis will be performed as appropriate. % liver fat as well as other secondary PD/biomarker endpoints will be analyzed similarly.

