## **12.5 Analysis of secondary endpoints**

### **12.5.1 Efficacy and/or Pharmacodynamic endpoint(s)**

A mixed-effect model for repeated measures analysis (MMRM) will be conducted for log-transformed ratio to baseline ELF Test and ALT. Commercially Confidential Information

An unstructured variance-covariance matrix will be used to account for correlation among multiple measurements from the same participant and variance heterogeneity. If the unstructured covariance causes model convergence issues, then other simpler covariance structures will be considered. Least squares mean, the associated 2-sided 80% confidence interval and the p-value will be obtained for each treatment at each visit and back transformed to the original scale. Contrasts assessing trend over time will be constructed for each treatment using various functional forms as needed. Both cohort-wise and combined cohort analysis will be performed as appropriate.

Log-transformed ratio to baseline % liver fat, hsCRP, HOMA-IR, fasting glucose, fasting insulin, and fasting lipid profile, as well as change from baseline ELF Test, ALT, % liver fat, waist circumference, hip circumference, waist-to-hip ratio, and % change from baseline weight will also be analyzed. Parameters with more than one post-treatment measurement will be subjected to the same MMRM analysis described above for ELF Test and ALT using untransformed baseline in lieu of log-transformed baseline as a covariate for the untransformed data analysis. For parameters with only one post-treatment measurement such as % liver fat, an ANCOVA with treatment and stratification factor (race and BMI group) as classification factors and baseline (or log-transformed baseline if applicable) as a covariate will be employed.

Additionally, a multivariate ANCOVA will be done for the three-dimensional endpoint: log-transformed ratio to baseline ELF Test, ALT and % liver fat at Week 12. The model will include treatment and stratification factor (race and BMI group) as classification factors and log-transformed baseline as a covariate. An arbitrary 3 by 3 covariance matrix will be assumed for the three-dimensional endpoint.

Proportion of participants with at least 30% relative reduction and 5% absolute reduction in % liver fat will be tabulated separately by treatment. If there are sufficient data, then a subgroup analysis (ANCOVA) in participants with baseline liver fat  $\geq 10\%$  will be performed to compare % liver fat between treatments.

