#### **17.1.1.3 Rationale for the single treatment**

The LYS006 CCI single treatment arm will allow assessment of LYS006 safety, tolerability and efficacy and comparison of data to LYS006 combination in order to determine whether the single agent effects are additive, synergistic or antagonistic.

Commercially Confidential Information

---

Commercially Confidential Information

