## **5.3 Statistical model, assumptions and hypotheses**

Comercially Confidential Information

An unstructured variance-covariance structure will be used. If the unstructured covariance causes model convergence issues, then other simpler covariance structures will be considered in the following sequence: TOEP, AR(1) and CS. The least squares mean differences between treatments and the associated 2-sided 90% confidence intervals in the logarithmic scale will be obtained at each visit and will then be back-transformed to the original scale to produce the geometric mean ratio (GMR) between treatments and associated 90% CIs at each visit and for each PK parameter. The associated p-value will also be obtained at each visit and for each PK parameter.

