### **6.2.3 Statistical model, assumptions and hypotheses**

A mixed-effect model for repeated measures (MMRM) analysis will be conducted for log-transformed ratio to baseline in ELF Test and ALT.

Commercially Confidential Information

An

unstructured variance-covariance matrix will be used to account for correlation among multiple measurements from the same participant and variance heterogeneity. If the unstructured covariance causes model convergence issues, then other simpler covariance structures will be considered. Least squares mean, the associated 2-sided 80% confidence interval and the p-value will be obtained for each treatment at each visit and back transformed to the original scale, meaning that the least squares means will be expressed as geometric means after the back-

transformation on the original scale. Contrasts assessing trend over time will be constructed for each treatment using various functional forms as needed. Both cohort-wise and combined cohort analysis will be performed as appropriate.

Log-transformed ratio to baseline in % liver fat, hsCRP, HOMA-IR, HbA1c, fasting glucose, fasting insulin and fasting lipid profile as well as change from baseline in ELF Test, ALT and % liver fat, waist circumference, hip circumference, waist to hip ratio and percentage change from baseline in body weight will also be analyzed. Parameters with more than one post-treatment measurement will be subjected to the same MMRM analysis described above for ELF Test and ALT using untransformed baseline in lieu of log-transformed baseline as a covariate for the untransformed data analysis.

Commercially Confidential Information

Additionally, a multivariate ANCOVA will be done for the three-dimensional endpoint: log-transformed ratio to baseline in ELF Test, ALT and % liver fat at Week 12. The model will include treatment and stratification factor (race and BMI group at baseline) as classification factors and log-transformed baseline as a covariate. An arbitrary 3 by 3 covariance matrix will be assumed for the three-dimensional endpoint.

If there are sufficient data, then a subgroup analysis (ANCOVA) in participants with baseline liver fat  $\geq 10\%$  will be performed to compare % liver fat between treatments.

Commercially Confidential Information

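### LYS006 alone is to be compared with LYS006 + tropifexor, but the readable efficacy text does not specify that contrast for ELF, ALT or full-set liver fat

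*Protocol*

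**What the plan says.** **The comparison promised.** Protocol 4.3 allows single-drug arms where a drug's effect on the relevant biomarkers has not been measured before, and says that in such a case "the treatment effects of the single drug treatment arm would be compared to both the combination drug effects and the historical placebo effects". Cohort 1, Arm 1 is a single-drug arm. For it, protocol 17.1.1.3 gives as a purpose "comparison of data to LYS006 combination in order to determine whether the single agent effects are additive, synergistic or antagonistic". Protocol 17.1 plans about 50 participants randomised 1:1 to the two arms.

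**The efficacy outputs stated.**
- For the log ratio to baseline in ELF and ALT, protocol 12.5.1 says: "Least squares mean, the associated 2-sided 80% confidence interval and the p-value will be obtained for each treatment at each visit". The protocol summary and SAP 6.2.3 carry the same statement. Trend contrasts over time are also defined within each treatment.
- For full-set liver fat, protocol 12.5.1 gives a model but no output: "For parameters with only one post-treatment measurement such as % liver fat, an ANCOVA with treatment and stratification factor (race and BMI group" as classification factors, with baseline as covariate. The protocol summary adds only that liver fat is handled in a similar way to ELF and ALT.
- Protocol 12.5.1 and SAP 6.2.3 also plan a multivariate ANCOVA of ELF, ALT and liver fat at Week 12, with treatment as a factor. No contrast, interval or test is named for it.
- If there are enough data, an ANCOVA in participants with baseline liver fat of at least 10% "will be performed to compare % liver fat between treatments". This is the only readable efficacy analysis described as a comparison between treatments.

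**How the SAP writes such a contrast for PK.** SAP 5.3: "The least squares mean differences between treatments and the associated 2-sided 90% confidence intervals in the logarithmic scale will be obtained at each visit", then back-transformed to geometric mean ratios.

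**The concern.** The plan gives a reason for running the LYS006-alone arm, but in readable text it does not name the estimate that would serve that reason. If the stated outputs are followed literally, the two arms can be compared only by placing two one-arm results next to each other.

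That is a poor comparison for two reasons. First, one arm having a small p-value and the other not is weak evidence that the arms differ, and judging by overlap of two intervals applies a different and stricter test. Second, a change from baseline within one arm mixes drug effect with anything that moves both arms, such as regression to the mean after entry on raised ALT, or general care during the study. Protocol Table 4-2 shows that placebo groups themselves moved: the listed ALT changes run from -13.4% to +35.5%. A concurrent between-arm contrast removes shifts common to both arms, and per-arm p-values do not.

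The study is open label, so it helps to fix the comparison before results are seen.

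**Working it through.** **1. Is there a figure to reproduce?** No effect size, SD or power is readable, so the sample size cannot be re-derived. The counts agree with each other: protocol section 5 expects about 25 enrolled and 20 evaluable per arm. That implies 20% non-evaluable: 20 / (1 - 0.20) = 25, and 2 x 25 = 50, as in section 17.1.

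**2. Can the existing model give the contrast?** Yes. The protocol summary says: "The model will include effects for treatment, visit, treatment by visit interaction, stratification factor (race and BMI group" and baseline terms. With treatment and treatment-by-visit in the MMRM, and treatment in the ANCOVA, the difference between arms is a linear combination of terms already fitted.

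**3. What precision would it have?** Inputs: n = 20 per arm (section 5), two-sided 80% interval (12.5.1), z = 1.2816, equal SD in both arms.
- Per arm: half-width = 1.2816 x SD / sqrt(20) = 0.287 SD.
- Difference: half-width = 1.2816 x SD x sqrt(2/20) = 0.405 SD (0.412 SD with a t quantile).
- Ratio of the two half-widths: sqrt(2) = 1.414.
- Difference detectable with 80% power at two-sided 20%: (1.2816 + 0.8416) x sqrt(2/20) = 0.67 SD.

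The documents give no log-scale SD. Over an assumed range, the 80% interval on the geometric mean ratio is the estimate multiplied and divided by exp(0.405 x SD):

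| Assumed log-scale SD | 0.2 | 0.3 | 0.4 | 0.5 |
|---|---|---|---|---|
| Factor | 1.08 | 1.13 | 1.18 | 1.22 |

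**4. Can per-arm p-values stand in for the contrast?** This is an illustration. It assumes independent arms, equal standard errors, a normal approximation, n = 20 per arm, and a per-arm test of no change from baseline. Suppose both arms have the same true change d, in SD units. The chance that one arm reaches p < 0.20 is

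p = Phi(d x sqrt(20) - 1.2816) + Phi(-d x sqrt(20) - 1.2816),

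and the chance that exactly one of the two does so is 2p(1 - p).

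| True change in both arms (SD) | p | Exactly one arm reaches p < 0.20 |
|---|---|---|
| 0 | 0.200 | 32% |
| 0.2 | 0.364 | 46% |
| 0.287 | 0.506 | 50% |
| 0.5 | 0.830 | 28% |

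**5. Can interval overlap stand in for it?** Same assumptions. Two 80% intervals fail to overlap when the difference exceeds 2 x 1.2816 = 2.563 per-arm standard errors. The standard error of the difference is 1.414 times the per-arm one, so the criterion is z = 2.563 / 1.414 = 1.812, a two-sided level of about 7% where 20% was intended. For a true difference that the direct contrast would detect with 80% power (1.2816 + 0.8416 = 2.123 standard errors of the difference), power under the overlap rule is Phi(2.123 - 1.812) = 62%.

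**The case against.** The strongest objection is redaction. Text is blacked out after the first MMRM sentence in protocol 12.5.1 and SAP 6.2.3, where the SAP's ANCOVA for single-measurement endpoints would sit, and directly after the subgroup sentence in both documents. Section 4.3 also has redacted text before the sentence on comparisons. The contrast may be in one of these places. The protocol summary appears to show what the first of these redactions holds (model terms), but it is a condensed text that also omits the multivariate ANCOVA and the subgroup analysis, so its silence proves little about the rest. A reader might infer that the between-arm contrast is never estimated; the documents do not support that.

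Other parts of the objection also stand:
- The Week 12 multivariate ANCOVA has treatment as a factor, and in a two-arm cohort that factor is a joint between-arm effect on these three endpoints. With no output stated, however, it does not promise an estimate and interval for each endpoint.
- The full-set liver-fat ANCOVA states no output, so calling it per-arm only would be an inference. It can equally be read like the subgroup ANCOVA, as comparing treatments. Either way the output is unstated.
- The contrast is not wholly randomised. Protocol 6.3.2 allows enrolment without randomisation when only one arm is open or a participant is eligible for only one arm. Analysis is by treatment received, with exclusions for protocol deviations.
- Nothing readable says that arms will be compared by discordant significance or by overlap. The figures in steps 4 and 5 show what those habits would cost and do not describe a stated procedure.
- The study is non-confirmatory, its primary objective is safety, and display details are left to separate table shells. Uncontrolled per-arm p-values are unremarkable in that setting.

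These points limit the wording and the weight of the concern. None of them supplies the contrast in readable text.

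**Conclusion.** The concern holds as a gap in the readable specification. Two protocol sections promise a comparison of LYS006 alone with the combination. The readable efficacy text names per-arm outputs for ELF and ALT and no output for the full-set liver-fat ANCOVA or the multivariate ANCOVA. The same SAP does specify treatment differences for PK. Whether redacted text closes the gap cannot be determined.

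At 20 evaluable per arm the direct contrast would have an 80% half-width of about 0.41 SD, which is useful for an exploratory study. Relying on per-arm significance could give apparently different arms in 28% to 50% of trials when the true changes are equal. That range rests on assumed changes of 0 to 0.5 SD, equal standard errors and a normal approximation.

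The change is worth making because it costs almost nothing and serves the stated purpose of the arm. It would estimate the increment from adding tropifexor. It would not by itself settle additivity or synergy, since Cohort 1 has no tropifexor-alone arm.

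**What to change.** The sponsor should first confirm whether redacted text already specifies the contrast. If it does not, add to protocol 12.5.1 and SAP 6.2.3:

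> The LS mean difference between tropifexor + LYS006 and LYS006 (a geometric mean ratio for log-scale endpoints), with its 2-sided 80% CI and p-value, will be reported in the full efficacy/PD analysis set. It will come from the same MMRM for ELF and ALT, at each visit, and from the same ANCOVA for % liver fat and other endpoints with a single post-treatment measurement. Conclusions about differences between the arms will rest on this contrast and not on the per-arm p-values. Participants enrolled without randomisation will be [left out of the contrast / included, with a sensitivity analysis that leaves them out].

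One of the two bracketed options should be chosen in advance. It would also help to say what the multivariate ANCOVA will report.

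Cost: a few sentences and one extra contrast per model, with no new data, visits or participants. The protocol wording needs an amendment under section 14.1. New cohorts are added by substantial amendment anyway, so it could go in with one of those.
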